## **10.2 Screening Procedures**

Procedures to be completed within 28 days prior to first treatment (day 1) (unless otherwise noted).

- Informed consent
- Review of eligibility criteria-
- Recording of medical history and concomitant medications
- Physical exam (including weight)
- ECG
- Vital signs (blood pressure, temperature, pulse and respirations)
- Radiographic imaging (chest, abdomen, and pelvis and all other sites of disease)
- Imaging of primary tumor site

### Laboratory Assessments

Procedures to be completed within 28 days prior to enrollment

- CBC w/diff
- CMP and uric acid
- PT/INR, PTT., Urine pregnancy test for females of childbearing potential within 7 days of W1D1

## **10.3 Post-treatment Evaluations**

Following surgical resection of primary tumor, patients will be followed as per NCCN guidelines for approximately 2 years for survival data and disease recurrence.

# **11. MEASUREMENT OF EFFECT**

## **11.1 Pathologic Response**

4 to 6 weeks after the end of neoadjuvant therapy, patients will undergo resection of the treated tumor. The SOC pretreatment biopsy and all the resected tumor samples will be reviewed by the same pathologist.

The percentage of post treatment tumor necrosis must be documented. The primary end point for this study is pathologic complete response (pCR), and is defined as  $\geq 95\%$  tumor necrosis following concurrent radiation therapy and ascorbate

Treatment effect on the resected overlying skin tissue will be graded and recorded (to be done by the pathologist). This will be compared with historical controls.

Additional immunohistochemical studies will be performed as determined by the pathologist.

## **11.2 Time to Disease progression (TTP)**

TTP is defined as the time from Enrollment until objective tumor progression including local and distant recurrences.

## **11.3 Other Response Parameters**

The following response assessment guidelines may be amended during the course of the study if changes are made to the current RECIST Guidelines or if a new disease assessment tool becomes available.

**Response Measurement Criteria:**

Measurements of the tumor in its largest dimension should be obtained at baseline and at the end of the treatment phase, prior to surgical resection.

Response criteria should be by RECIST v 1.1.

- Complete response is the disappearance of all target lesions.
- Partial response is a 30% decrease in the sum of the longest dimensions of the target lesions, relative to baseline.
- Progressive disease is an increase of 20% or more in the sum of the longest dimension of target lesions
- Stable disease is a decrease in the tumor size of < 30% or an increase of < 20%.
- Antitumor response by pathologic assessment will be performed on the resected tumors. Pathologic assessment will be performed per institutional guidelines.
- The percent of tumor necrosis and the percent of tumor-infiltrating lymphocytes will be documented.
- Complete pathological response will be considered  $\geq 95\%$  pathologic tumor necrosis.

Radiologic response will be evaluated in this study using the new international criteria proposed by the revised Response Evaluation Criteria in Solid Tumors (RECIST) guideline (version 1.1) [*Eur J Ca* 45:228-247, 2009]. Changes in the largest diameter (unidimensional measurement) of the tumor lesions and the shortest diameter in the case of malignant lymph nodes are used in the RECIST criteria.

## 12. STATISTICAL CONSIDERATIONS

### 12.1 Phase Ib

The primary objective of the Phase Ib portion of this study is to confirm the current standard dose of intravenous ascorbate, 75 gm, utilized in patients diagnosed with pancreatic cancer also receiving concurrent chemo radiation is safe within this population of sarcoma patients being treated concurrently with pre-operative radiation. Up to six (6) patients will be recruited to the standard dose, 75 grams administered intravenously 3 times a week during radiation therapy (5 weeks). If at most 1 out of 6 patients experience a DLT, the standard dose will be considered safe. If 2 or more patients experience a DLT, the next cohort of patients will be assigned to dose level - 1. The recommended phase II dose (RP2D) will be defined as the highest dose level for which at most 1 out of 6 patients experience a DLT.

### 12.2 Phase II

The primary objective of the Phase II portion of this study is to evaluate the proportion of patients with pathologic tumor necrosis  $\geq 95\%$ . Previous literature indicates approximately 10% of patients will achieve  $\geq 95\%$  tumor necrosis with pre-operative radiation therapy alone. A sample size of 25 patients achieves 81% power to detect a difference of 20% (from 10% to 30%) using a one-sided binomial exact test. The target significance level is 0.05 and the achieved level is 0.03. If 6 or more patients achieve  $\geq 95\%$  tumor necrosis, the treatment will be deemed worthy of further investigation. For secondary objectives, time to disease progression and overall survival will be estimated using the Kaplan-Meier method. Estimated survival probabilities will be plotted and medians reported, along with 95% confidence intervals. To identify differences in wound complication and Grade 3-4 dermatitis rates relative to historical controls, binomial point estimates and 95% exact confidence intervals will be reported. Mixed effects regression models will be used to estimate changes in labile iron and diffusion imaging sequences on MRI pre and post treatment.

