## 5. TREATMENT PLAN AND STUDY SCHEMA

### 5.1 Study Design

This is a single-arm open-label phase Ib/II clinical study assessing the efficacy of concurrent high dose ascorbate in combination with radiotherapy in patients with locally advanced, resectable, high grade sarcomas, as measured by pathological response rates. Patients will be treated with three times weekly IV ascorbate concurrently with radiation therapy. Surgery will be performed 4-6 weeks from the end of radiation therapy to allow for resolution of acute toxicities per current standard of care.

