## Ascorbate Dose Levels

[figure not shown]
Dose 0      Ascorbate 75 gm IV three times weekly concurrently with radiation  
Dose -1      Ascorbate 62.5 gm IV three times weekly concurrently with radiation  
•      Initial dose for all = Ascorbate 75gm IV

## 5.3 Phase 2

[figure not shown]
The phase 2 part of the study will provide an estimate of the relative treatment effect of pharmacological ascorbate in combination with preoperative EBRT in subjects with locally advanced, resectable, extremity or retroperitoneal high grade sarcomas, as measured by pathological response rates.

As above, patients will receive the first dose of pharmacological ascorbate intravenously on day 1 of week 1 provided no reactions are seen to the test dose. This will be followed by 3 times a week dosing (= 15 doses total) at Dose 0 until completion of EBRT. Standard doses of radiation for resectable soft tissue sarcomas according to the NCCN sarcoma guidelines will be administered. Patients will receive preoperative radiation at a dose of 50 Gy over 25 fractions for extremity and trunk sarcoma or 45 to 50.4 Gy in 28 fractions for retroperitoneal sarcomas starting on week 1 day 1. Subjects should be followed either by clinic visit or phone contact every 12 weeks (+/- 4 weeks) for approximately 24 months after the end of the treatment phase, at which time the initial survival data and disease recurrence will be assessed. Details as per study calendar (Section 10).

[figure not shown]

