## 7.5 Serious Adverse Event Reporting to DSMC

For any experience or condition meeting the definition of a serious adverse event (SAE; 21CFR312.32), from the first day of study treatment and typically continue through the 30 day follow-up period after treatment is discontinued.

Investigators must report to the DSMC any SAE, regardless of attribution to study drug. SAEs must be reported *via* an OnCore SAE Report within 1 business day of learning of the event.

An adverse event is considered **serious** if it results in ANY of the following outcomes:

- Death
- A life-threatening adverse event
- An adverse event that results in inpatient hospitalization OR prolongation of existing hospitalization for  $\geq 24$  hours
- A persistent or significant incapacity or substantial disruption of the ability to conduct normal life functions
- A congenital anomaly/birth defect.
- Important Medical Events (IME) that may not result in death, be life threatening, or require hospitalization may be considered serious when, based upon medical judgment, they may jeopardize the patient or subject and may require medical or surgical intervention to prevent one of the outcomes listed in this definition. ([21 CFR 312.32](#); [ICH E2A](#) and [ICH E6](#)).

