## 10. STUDY CALENDAR

### 10.1 Study Procedures

	Screen b	Treatment a					Off treatment and end of study c	Follow Up d
		Week 1	Week 2	Week 3	Week 4	Week 5 (+1wk j )		
H & P	X	X		X		X		
Tumor biopsy (optional)	X b							
Performance status	X						X	X
Clinical MRI/ Staging CT	X						X	X e
Pregnancy test k (urine)	X							
G6PD	X							
EKG	X							
CBC w/diff	X			X		X		
PT/INR, PTT & uric acid	X							
Height	X							
Weight, BSA	X						X	
Vitals (BP, pulse) m	X	X	x	X	x	X	X	
Comprehensive metabolic panel (CMP)	X	X		X		X	X	
Ascorbate infusion	X i	XXX	XXX	XXX	XXX	XXX		
Blood for ascorbate levels f	X	X		X		X		
ROS Research blood g	X	X		X		X	X	
Immunology research lab g	X					X	X	
Iron Panel including ferritin h	X						X	
T2* /QSM and DWI MR imaging sequences (optional)	X			X			X	
Adverse Events & Con Meds			X	X	X	X	X	

**a** study day 1 is defined as radiation therapy day 1 (i.e., fraction 1).

**b** screening labs, history, and physical must be obtained  $\leq$  28d from d1. G6PD may be obtained at any time prior to test dose. MRI/CT obtained  $\leq$  28d from d1 (RT sim is acceptable). Pregnancy test per institutional guidelines. Optional tumor biopsy can be done anytime before week 1 dosing.

**c** includes both off-treatment evaluation and study completion. Study completion requires a final study dictated visit 4 to 6 weeks after the last dose of ascorbate. Follow at least monthly until resolution of all ascorbate related adverse events.

**d** approx every 3 months (every 12 weeks [+/- 4 weeks]) for overall survival through passive chart review, phone call or scheduled follow-up visit for 2 years

**e** Imaging as per standard of care for site specific sarcomas

**f** 4cc green-top Na-Heparin tube. Draw pre-infusion at 15g dose, then 30 min post-infusion: week 1 day 1 , week 3 and last infusion of week 5

**g** 6cc pink-top EDTA tube. Draw pre infusion The specimen should be placed on ice immediately after draw and carried to the lab

**h** At time of screening and end of study

**i** Test dose of 15 g intravenously once G6PD levels confirmed to be adequate. A physician must review the patient's medication list against the list of medications prohibited on this trial prior to the test dose of ascorbate.

**j** In case of radiation treatment delays due to holidays

**k**  $\pm 7$  days prior to day 1

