### **Routine Adverse Event Reporting**

For non-serious Adverse Events, documentation must begin from the time the subject signs the informed consent document and continue through the 30-day follow-up period after the last dose of study drug.

Collected information should be recorded in the electronic/Case Report Forms (eCRF/CRF) for that subject. A description of the event, its severity or toxicity grade (according to [NCI's Common Toxicity Criteria \(CTCAE\)](#)), onset and resolved dates (if applicable), and the relationship to the study drug should be included. Documentation should occur in real time. The principal investigator has final responsibility for determining the attribution of the event as it is related to the study drug.

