### **Serious Adverse Event Reporting**

For any experience or condition that meets the definition of a serious adverse event (SAE), recording of the event must begin after signing of the informed consent and continue through the 30 day follow-up period after treatment is discontinued.

Investigators must report to the DSMC any serious adverse events (SAE), whether or not they are considered related to the investigational agent(s)/intervention (21 CFR 312.64). SAEs must be reported via an OnCore SAE Report within 24 hours of learning of the event.

An adverse event is considered **serious** if it results in ANY of the following outcomes:

1. Death
2. A life-threatening adverse event
3. An adverse event that results in inpatient hospitalization OR prolongation of existing hospitalization for  $\geq$  24 hours
4. A persistent or significant incapacity or substantial disruption of the ability to conduct normal life functions
5. A congenital anomaly/birth defect.
6. Important Medical Events (IME) that may not result in death, be life threatening, or require hospitalization may be considered serious when, based upon medical judgment, they may jeopardize the patient or subject and may require medical or surgical intervention to prevent one of the outcomes listed in this definition. (FDA, [21 CFR 312.32](#); [ICH E2A](#) and [ICH E6](#)).

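### Wound complications are to be compared with historical controls, but the event is not defined and the written adverse event windows close around or before surgery

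*Combined protocol and SAP*

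**What the plan says.** **The comparison.** Section 12.2 of the combined protocol and SAP will report binomial estimates with exact 95% intervals "To identify differences in wound complication and Grade 3-4 dermatitis rates relative to historical controls". Dermatitis has a grade threshold; wound complication has none. Sections 3 and 3.2 list radiation-related skin toxicity but not wound complications.

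**Reference rates.** Section 1.4 cites 35% acute wound complications with preoperative radiation in a trial in extremity sarcoma, and 25% to 44% across retrospective series. Section 5.7.11 expects wound complications of any grade in roughly a third of patients. Section 12.2 does not say which figure is the comparator.

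**Timing.**
- Section 5.1: "Surgery will be performed 4-6 weeks from the end of radiation therapy".
- Sections 5.2 and 5.7: ascorbate runs until radiation ends. Section 5.3 gives "15 doses total) at Dose 0 until completion of EBRT".
- Appendix D, routine adverse events: recording must "continue through the 30-day follow-up period after the last dose of study drug".
- Appendix D, serious adverse events: "continue through the 30 day follow-up period after treatment is discontinued". Section 7.5: "typically continue through the 30 day follow-up period after treatment is discontinued".
- Section 10.1, footnote c: "Study completion requires a final study dictated visit 4 to 6 weeks after the last dose of ascorbate". This is the last calendar column with an adverse event mark. The same footnote continues follow-up beyond it only for events related to ascorbate.
- Section 10.1, footnote d: later contacts are "for overall survival through passive chart review, phone call or scheduled follow-up visit for 2 years". Sections 5.10 and 10.3 add disease recurrence.

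**The concern.** A surgical wound complication can occur only after resection. The plan describes recording that ends near or before resection, followed by contacts whose stated purpose is survival and recurrence. If the Section 12.2 rate is drawn from that recording, its denominator is all treated patients while its numerator covers almost no time at risk. Setting it against series that report 25% to 44% would make the combination look safer for wounds than it is, and could hide a real increase.

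The missing definition matters separately. A broad any-grade count set against a narrower historical definition would bias the comparison the other way. With definition, interval and comparator all open, each could be settled after the data are seen.

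Section 1.4 cites high toxicity rates as a reason to improve the safety of neoadjuvant radiotherapy, so a misleadingly low rate bears on the trial's own rationale.

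**Working it through.** **1. The plan's own figures.** The only computed figures in Section 12.2 are for pCR: n = 25, success if 6 or more respond, 10% against 30%. Exact binomial: P(X ≥ 6 | 25, 0.10) = 0.033 and P(X ≥ 6 | 25, 0.30) = 0.807. These match the stated 0.03 and 81%, and this point does not touch them. Section 12.2 gives no precision or reference rate for wound complications.

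**2. Day count when ascorbate ends on the last radiation day.** Surgery is on day 28 to 42 after radiation.
- Routine window minus surgery: 30 − 28 = +2 days, to 30 − 42 = −12 days.
- Calendar visit (day 28 to 42) minus earliest surgery: 42 − 28 = 14 post-operative days at most, and none if surgery follows the visit.

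**3. Day count for 28 fractions with ascorbate stopped after 15 doses.** Assumes a Monday start, a last dose on the Friday of week 5, and no delay.
- Last dose day 33; radiation ends day 38; window closes day 33 + 30 = 63.
- Surgery on day 38 + 28 = 66 to 38 + 42 = 80, so the window closes 3 to 17 days before surgery.
- Visit on day 61 to 75, so at most 75 − 66 = 9 post-operative days.

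**4. What under-capture could do (illustration).** The documents do not say when wound events occur, so the captured fraction f is an assumption shown as a range. Recorded events follow Binomial(n, p × f), with true rate p equal to the historical rate.

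Clopper-Pearson 95% upper limits at n = 25: 0 events 13.7%, 1 event 20.4%, 2 events 26.0%, 3 events 31.2%, 4 events 36.1%. So 3 or fewer recorded events would appear to exclude 35%. The expected number at full capture is 25 × 0.35 = 8.75.

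Chance that the interval lies wholly below the reference:

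| n | Reference and true rate | Events needed | f = 1 | f = 0.75 | f = 0.50 | f = 0.25 |
|---|---|---|---|---|---|---|
| 25 | 35% | ≤ 3 | 1.0% | 7.5% | 34% | 83% |
| 25 | 25% | ≤ 1 | 0.7% | 3.8% | 16% | 53% |
| 25 | 44% | ≤ 5 | 1.1% | 12% | 52% | 95% |
| 20 (assumed extremity subgroup) | 35% | ≤ 2 | 1.2% | 7.3% | 29% | 75% |
| 15 (assumed extremity subgroup) | 35% | ≤ 1 | 1.4% | 6.6% | 23% | 62% |

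**5. Missed harm, n = 25, reference 35%.** The lower limit is 34.9% with 14 events and 38.7% with 15, so 15 or more are needed.
- Assumed true rate 60%: P(X ≥ 15) = 59% at full capture and 0.2% at f = 0.50.
- Assumed true rate 50%: 21% and 0.02%.

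**The case against.** The strongest reply is that the plan is silent rather than wrong. Nothing says the Section 12.2 rate must come from the adverse event windows. The eCRFs, which the principal investigator and statistician approve (Appendix D), are not in the documents and may hold a wound item. Chart review could recover events. All of this stands: the under-count is conditional. But no passage plans such collection, and even perfect chart review would leave definition, interval and comparator open.

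For serious events, treatment being discontinued could be read to include surgery. Section 11.3 argues against that by placing the end of the treatment phase before resection. Non-serious events would be missed on either reading.

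The blank Follow Up cell in the calendar's adverse event row is weak evidence alone, since the row is also blank at screening and week 1, although Appendix D starts routine adverse event recording at consent. The written windows carry the argument.

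CTCAE v5 (Section 7.1) and the any-grade remark in Section 5.7.11 supply a grading scale and an expected rate. Neither selects a wound term or threshold for the endpoint, or ties it to the historical definitions.

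The probabilities rest on assumed capture fractions, and Section 12.2 sets no rule for excluding 35%. That is fair. It is also fair that at a true rate of 50% even full capture has only a 21% chance of showing harm, a limit of n = 25 that better recording does not remove.

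**Conclusion.** The concern holds. It is certain that the documents neither define wound complications for the Section 12.2 comparison nor schedule their post-operative collection. It is also certain, by day count, that the routine window covers at most 2 post-operative days and the last visit marked for adverse events at most 14.

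The under-count follows if the rate is taken from those sources. Its size cannot be derived from the documents; the tabulated probabilities show only how sensitive the comparison is to lost events. With nothing recorded, 0 of 25 gives an upper limit of 13.7%, below the whole 25% to 44% range.

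This is a descriptive secondary safety comparison, so the consequence is a misleading safety statement rather than a wrong trial decision. It should be corrected before the comparison is made.

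**What to change.** 1. **Section 12.2:** define the wound complication event, its grade threshold and its post-operative interval so that they match one named historical source, and state the reference rate.
2. **Section 7.5, Appendix D and the Section 10.1 calendar:** extend recording of wound complications, as data collection only, from surgery through that interval, by chart abstraction or at post-operative contacts that already take place.
3. **Section 3:** list the endpoint.
4. **Comparator by site:** apply the 35% to extremity tumours only and report other sites separately. Do not assume that 25% to 44% applies to retroperitoneal tumours: the cited titles include lower-extremity and extremity/superficial-trunk series, and none names retroperitoneal tumours. This step is secondary; items 1 to 3 stand without it.

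Separately, the 15-dose total and the instruction to continue until radiation ends need reconciling for 28-fraction courses, because the last dose starts the routine window.

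**Cost:** amendment wording, one eCRF item and chart abstraction for up to 25 patients. No new visit or procedure is needed if the interval can be covered from charts or existing contacts. Reporting by site widens the extremity interval. Precision stays limited even with full capture: 9 of 25 gives 36%, with an exact 95% interval of 18.0% to 57.5%.

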### 12.3 Sample Size/Accrual Rate

The Phase I portion of this study is expected to require 6 evaluable patients (min 6, max 12). Patients treated in Phase Ib at the RP2D will also be included in the Phase II portion. Additional evaluable patients will be accrued for a total of 25 patients treated at the RP2D. The anticipated accrual rate is 2 patients per month who would meet inclusion criteria.

## PROTOCOL APPENDIX A: Performance status criteria

ECOG Performance Status Scale		Karnofsky Performance Scale	
Grade	Descriptions	Percent	Description
0	Normal activity. Fully active, able to carry on all pre-disease performance without restriction.	100	Normal, no complaints, no evidence of disease.
		90	Able to carry on normal activity; minor signs or symptoms of disease.
1	Symptoms, but ambulatory. Restricted in physically strenuous activity, but ambulatory and able to carry out work of a light or sedentary nature (e.g., light housework, office work).	80	Normal activity with effort; some signs or symptoms of disease.
		70	Cares for self, unable to carry on normal activity or to do active work.
2	In bed <50% of the time. Ambulatory and capable of all self-care, but unable to carry out any work activities. Up and about more than 50% of waking hours.	60	Requires occasional assistance, but is able to care for most of his/her needs.
		50	Requires considerable assistance and frequent medical care.
3	In bed >50% of the time. Capable of only limited self-care, confined to bed or chair more than 50% of waking hours.	40	Disabled, requires special care and assistance.
		30	Severely disabled, hospitalization indicated. Death not imminent.
4	100% bedridden. Completely disabled. Cannot carry on any self-care. Totally confined to bed or chair.	20	Very sick, hospitalization indicated. Death not imminent.
		10	Moribund, fatal processes progressing rapidly.
5	Dead.	0	Dead.

